1.2. Study Schema

The study schema is presented in [Figure 1](#).

Figure 1: Study Schema

Abbreviations: COVID-19 = coronavirus disease 2019; mRNA = messenger ribonucleic acid; N = number.

1.3. Schedule of Events

Table 1: Schedule of Events Part 1

Visit Number		1	2			3	4	5		6	USV
Type of Visit	C	C	SC	SC	C	C	C	SC	C	C	
Month Timepoint		M0			M1	M3	M6	M9	M12	Up to M12	
Study Visit Day	Screening ¹	D1 (Baseline)	D8	D15	D22	D29	D85	D179	D269	D359/EoS	USV
Window Allowance (Days)	-28		+3	+3	+3	-3/+7	±7	±14	±7	±14	N/A
Days Since Vaccination	-	0	7	14	21	28	84	178	268	358	
ICF, demographics, concomitant medications, medical history ²	X										
Confirm participant meets inclusion and exclusion criteria	X	X									
Physical examination ³	X	X				X	X	X		X	X
Vital signs ⁴	X	X									X
Pregnancy testing ⁵	X	X									
Randomization		X									
Dosing											
Study injection (including 15-minute post-dosing observation period)		X									
Surveillance for COVID-19											

Visit Number		1	2			3	4	5		6	USV
Type of Visit	C	C	SC	SC	C	C	C	SC	C	C	
Month Timepoint		M0			M1	M3	M6	M9	M12	Up to M12	
Study Visit Day	Screening ¹	D1 (Baseline)	D8	D15	D22	D29	D85	D179	D269	D359/EoS	USV
Window Allowance (Days)	-28		+3	+3	+3	-3/+7	±7	±14	±7	±14	N/A
Days Since Vaccination	-	0	7	14	21	28	84	178	268	358	
Surveillance for COVID-19/Unscheduled visit ⁶	X	X	X	X	X	X	X	X	X	X	X
Nasopharyngeal swab ⁶		X				X	X	X		X	X
Blood for SARS-CoV-2 surveillance		X				X	X	X		X	
eDiary activation for surveillance for COVID-19/Unscheduled visit						X					
eDiary prompts every 2 weeks for surveillance for COVID-19 and major changes in health						eDiary prompts every 2 weeks (Day 43 through Day 359/EoS)					
Immunogenicity Assessment											
Blood for humoral immunogenicity ⁷		X				X	X	X		X	

Visit Number		1	2			3	4	5		6	USV
Type of Visit	C	C	SC	SC	C	C	C	SC	C	C	
Month Timepoint		M0			M1	M3	M6	M9	M12	Up to M12	
Study Visit Day	Screening ¹	D1 (Baseline)	D8	D15	D22	D29	D85	D179	D269	D359/EoS	USV
Window Allowance (Days)	-28		+3	+3	+3	-3/+7	±7	±14	±7	±14	N/A
Days Since Vaccination	-	0	7	14	21	28	84	178	268	358	
Safety Assessments											
eDiary activation for recording solicited adverse reactions (7 days) ⁸		X									
Review of eDiary			X								
Follow-up safety			X	X	X				X		
Recording of Unsolicited AEs		X	X	X	X	X					
Recording of MAAEs, AESIs, AE leading to withdrawal and concomitant medications relevant to or for the treatment of these events ⁹		X	X	X	X	X	X	X	X	X	X
Recording of SAEs and concomitant medications relevant to or for the treatment of the SAE ⁹		X	X	X	X	X	X	X	X	X	X

Visit Number		1	2			3	4	5		6	USV
Type of Visit	C	C	SC	SC	C	C	C	SC	C	C	
Month Timepoint		M0			M1	M3	M6	M9	M12	Up to M12	
Study Visit Day	Screening ¹	D1 (Baseline)	D8	D15	D22	D29	D85	D179	D269	D359/EoS	USV
Window Allowance (Days)	-28		+3	+3	+3	-3/+7	±7	±14	±7	±14	N/A
Days Since Vaccination	-	0	7	14	21	28	84	178	268	358	
Recording of concomitant medications and non-study vaccinations ¹⁰		X	X	X	X	X	X	X	X	X	X

Abbreviations: AE = adverse event; AESI = adverse event of special interest; AR = adverse reaction; C = clinic visit; COVID-19 = coronavirus disease 2019; D = day; eDiary = electronic diary; EoS = end of study; ICF = informed consent form; M = month; MAAE = medically attended AE; N/A = not applicable; NP = nasopharyngeal; SAE = serious adverse event; SARS-CoV-2 = severe acute respiratory syndrome coronavirus 2; SC = safety (phone) call; USV = unscheduled safety visit.

All scheduled study visits should be completed within the respective visit windows. If the participant is not able to come on-site for a study site visit as a result of the COVID-19 pandemic (self-quarantine or disruption of study site activities following business continuity plans and/or local government mandates for “stay at home” or “shelter in place”), a safety call to the participant should be made in place of the study site visit. The safety call should encompass all scheduled visit assessments that can be completed remotely, such as assessment for AEs and concomitant medications. Home visits will be permitted for all non-dosing visits except for Screening if a participant cannot come to the study site.

1. The Screening Visit and Day 1 may be performed on the same day or a different day. Additionally, the Screening visit may be performed over multiple visits if within the 28-day screening window.
2. Verbal medical history is acceptable.
3. Physical examination: a full physical examination, including vital signs, height, and weight, will be performed at Screening and Day 1. Body mass index will be calculated at the Screening Visit only. Symptom-directed physical examinations will be performed on Day 29, Day 85, Day 179, D359/EoS, and during USV visits. On the day of the vaccination, the arm receiving the injection should be examined and the associated lymph nodes should be evaluated. Any clinically significant finding identified by a healthcare professional during a study visit should be reported as a MAAE.
4. Vital signs measurements: Systolic and diastolic blood pressures, heart rate, respiratory rate, and body temperature. The preferred route of temperature assessment is oral. On the day of vaccination, vital signs will be collected once before vaccination and once 15 minutes after vaccination. When applicable, vital sign measurements should be performed before blood collection. Participants who are febrile (body temperature $\geq 38.0^{\circ}\text{C}/100.4^{\circ}\text{F}$) before dosing must be rescheduled within the relevant window period to receive the injection. Afebrile participants with minor illnesses can be enrolled at the discretion of the investigator. Vital signs may be collected at other clinic visits in conjunction with a symptom-directed physical examination. A pulse oximeter measurement may be performed at the unscheduled visit, if applicable/available.

5. A point-of-care urine pregnancy test will be performed at the Screening Visit and before the vaccine dose on Day 1, if Day 1 is not on the same day as the Screening Visit. At the discretion of the investigator, a pregnancy test either via blood or point-of-care urine can be performed at any time. The participant's follicle stimulating hormone level should be measured at the Screening Visit, as necessary, and at the discretion of the investigator, to confirm postmenopausal status.
6. An unscheduled visit may be prompted by reactogenicity issues, illness visit for COVID-19, or new or ongoing AEs. If a participant experiences symptoms suggestive of COVID-19, the participant will be directed as soon as possible and within 24 hours to undergo testing as outlined in [Section 8.9.2](#). An unscheduled study illness visit will be arranged as soon as possible and within 72 hours for participants who test positive for SARS-CoV-2 as per testing as outlined in [Section 8.9.2](#). At this visit, an NP swab will be collected to evaluate for the presence of SARS-CoV-2 infection. If a study site visit is not possible, a home visit may be arranged to collect a swab sample and conduct clinical evaluations. Additionally, clinical information will be collected to evaluate the severity of the clinical case.
7. Samples for humoral immunogenicity must be collected prior to receipt of vaccination on Day 1. All participants will have blood drawn for humoral immunogenicity.
8. The participant will record data in the eDiary approximately 15 minutes after dosing while at the study site, with instruction provided by study staff. Study participants will continue to record in the eDiary each day after they leave the study site, preferably in the evening, on the day of dosing, and for 6 days following. Any solicited AR that is ongoing beyond Day 7 will be reported verbally by participants at the scheduled Safety Calls, until resolution. Adverse reactions recorded in eDiaries beyond Day 7 should be reviewed either via phone call or at the following study visit. Participants will be given thermometers to record their body temperatures and rulers to measure any injection site reactions.
9. Trained study personnel will call all participants to collect information relating to any MAAEs, AEs leading to study discontinuation, SAEs, AESIs, information on concomitant medications associated with those events, and any non-study vaccinations.
10. All concomitant medications and non-study vaccinations will be recorded through 28 days after vaccination, except authorized or investigational COVID-19 vaccine(s) given at any time during the study period should be recorded (Day 29 through EoS).

Table 2: Schedule of Events Part 2

Visit Number		1	2			3	4	5		6	USV
Type of Visit	C	C	C/SC	SC	SC	C	C	C	SC	C	C
Month Timepoint		M0				M1	M3	M6	M9	M12	Up to M12
Study Visit Day	Screening ¹	D1 (Baseline)	D8	D15	D22	D29	D85	D179	D269	D359/EoS	USV
Window Allowance (Days)	-28		+3	+3	+3	-3/+7	±7	±14	±7	±14	N/A
Days Since Vaccination	-	0	7	14	21	28	84	178	268	358	
ICF, demographics, concomitant medications, medical history ²	X										
Confirm participant meets inclusion and exclusion criteria	X	X									
Physical examination ³	X	X	X			X	X	X		X	X
Vital signs ⁴	X	X									X
Pregnancy testing ⁵	X	X									
Randomization		X									
Dosing											
Study injection (including 15-minute post-dosing observation period)		X									

Visit Number		1	2			3	4	5		6	USV
Type of Visit	C	C	C/SC	SC	C	C	C	SC	C	C	
Month Timepoint		M0			M1	M3	M6	M9	M12	Up to M12	
Study Visit Day	Screening ¹	D1 (Baseline)	D8	D15	D22	D29	D85	D179	D269	D359/EoS	USV
Window Allowance (Days)	-28		+3	+3	+3	-3/+7	±7	±14	±7	±14	N/A
Days Since Vaccination	-	0	7	14	21	28	84	178	268	358	
Surveillance for COVID-19											
Surveillance for COVID-19/Unscheduled visit ⁶	X	X	X	X	X	X	X	X	X	X	X
Nasopharyngeal swab ⁶		X				X	X	X		X	X
Blood for SARS-CoV-2 surveillance		X				X	X	X		X	
eDiary activation for surveillance for COVID-19/Unscheduled visit						X					
eDiary prompts every 2 weeks for surveillance for COVID-19 and major changes in health						eDiary prompts every 2 weeks (Day 43 through Day 359/EoS)					
Immunogenicity Assessment											
Blood for humoral immunogenicity ⁷		X				X	X	X		X	

Visit Number		1	2			3	4	5		6	USV
Type of Visit	C	C	C/SC	SC	C	C	C	SC	C	C	
Month Timepoint		M0			M1	M3	M6	M9	M12	Up to M12	
Study Visit Day	Screening ¹	D1 (Baseline)	D8	D15	D22	D29	D85	D179	D269	D359/EoS	USV
Window Allowance (Days)	-28		+3	+3	+3	-3/+7	±7	±14	±7	±14	N/A
Days Since Vaccination	-	0	7	14	21	28	84	178	268	358	
Blood for cellular immunogenicity in a subset of participants ⁷		X	X								
Safety Assessments											
eDiary activation for recording solicited adverse reactions (7 days) ⁸		X									
Review of eDiary			X								
Follow-up safety			X	X	X				X		
Recording of Unsolicited AEs		X	X	X	X	X					
Recording of MAAEs, AESIs, AE leading to withdrawal and concomitant medications relevant to or for the treatment of these events ⁹		X	X	X	X	X	X	X	X	X	X

Visit Number		1	2			3	4	5		6	USV
Type of Visit	C	C	C/SC	SC	C	C	C	SC	C	C	
Month Timepoint		M0			M1	M3	M6	M9	M12	Up to M12	
Study Visit Day	Screening ¹	D1 (Baseline)	D8	D15	D22	D29	D85	D179	D269	D359/EoS	USV
Window Allowance (Days)	-28		+3	+3	+3	-3/+7	±7	±14	±7	±14	N/A
Days Since Vaccination	-	0	7	14	21	28	84	178	268	358	
Recording of SAEs and concomitant medications relevant to or for the treatment of the SAE ⁹		X	X	X	X	X	X	X	X	X	
Recording of concomitant medications and non-study vaccinations ¹⁰		X	X	X	X	X	X	X	X	X	

Abbreviations: AE = adverse event; AESI = adverse event of special interest; AR = adverse reaction; C = clinic visit; COVID-19 = coronavirus disease 2019; D = day; eDiary = electronic diary; EoS = end of study; ICF = informed consent form; M = month; MAAE = medically attended AE; N/A = not applicable; NP = nasopharyngeal; SAE = serious adverse event; SARS-CoV-2 = severe acute respiratory syndrome coronavirus 2; SC = safety (phone) call; USV = unscheduled safety visit.

All scheduled study visits should be completed within the respective visit windows. If the participant is not able to come on-site for a study site visit as a result of the COVID-19 pandemic (self-quarantine or disruption of study site activities following business continuity plans and/or local government mandates for “stay at home” or “shelter in place”), a safety call to the participant should be made in place of the study site visit. The safety call should encompass all scheduled visit assessments that can be completed remotely, such as assessment for AEs and concomitant medications. Home visits will be permitted for all non-dosing visits except for Screening if a participant cannot come to the study site.

1. The Screening Visit and Day 1 may be performed on the same day or a different day. Additionally, the Screening visit may be performed over multiple visits if within the 28-day screening window.
2. Verbal medical history is acceptable.
3. Physical examination: a full physical examination, including vital signs, height, and weight, will be performed at Screening and Day 1. Body mass index will be calculated at the Screening Visit only. Symptom-directed physical examinations will be performed on Day 8 (if applicable), Day 29, Day 85, Day 179, D359/EoS, and during USV visits. On the day of the vaccination, the arm receiving the injection should be examined and the associated lymph nodes should be evaluated. Any clinically significant finding identified by a healthcare professional during a study visit should be reported as a MAAE.

4. Vital signs measurements: Systolic and diastolic blood pressures, heart rate, respiratory rate, and body temperature. The preferred route of temperature assessment is oral. On the day of vaccination, vital signs will be collected once before vaccination and once 15 minutes after vaccination. When applicable, vital sign measurements should be performed before blood collection. Participants who are febrile (body temperature $\geq 38.0^{\circ}\text{C}/100.4^{\circ}\text{F}$) before dosing must be rescheduled within the relevant window period to receive the injection. Afebrile participants with minor illnesses can be enrolled at the discretion of the investigator. Vital signs may be collected at other clinic visits in conjunction with a symptom-directed physical examination. A pulse oximeter measurement may be performed at the unscheduled visit, if applicable/available.
5. A point-of-care urine pregnancy test will be performed at the Screening Visit and before the vaccine dose on Day 1, if Day 1 is not on the same day as the Screening Visit. At the discretion of the investigator, a pregnancy test either via blood or point-of-care urine can be performed at any time. The participant's follicle stimulating hormone level should be measured at the Screening Visit, as necessary, and at the discretion of the investigator, to confirm postmenopausal status.
6. An unscheduled visit may be prompted by reactogenicity issues, illness visit for COVID-19, or new or ongoing AEs. If a participant experiences symptoms suggestive of COVID-19, the participant will be directed as soon as possible and within 24 hours to undergo testing as outlined in [Section 8.9.2](#). An unscheduled study illness visit will be arranged as soon as possible and within 72 hours for participants who test positive for SARS-CoV-2 as per testing as outlined in [Section 8.9.2](#). At this visit, an NP swab will be collected to evaluate for the presence of SARS-CoV-2 infection. If a study site visit is not possible, a home visit may be arranged to collect a swab sample and conduct clinical evaluations. Additionally, clinical information will be collected to evaluate the severity of the clinical case.
7. Samples for humoral immunogenicity and cellular immunogenicity (if applicable) must be collected prior to receipt of vaccination on Day 1. All participants will have blood drawn for humoral immunogenicity. Only a subset of participants who will receive the 4th dose as the study vaccine will have blood drawn for cellular immunogenicity.
8. The participant will record data in the eDiary approximately 15 minutes after dosing while at the study site, with instruction provided by study staff. Study participants will continue to record in the eDiary each day after they leave the study site, preferably in the evening, on the day of dosing, and for 6 days following. Any solicited AR that is ongoing beyond Day 7 will be reported verbally by participants at the scheduled Safety Calls, until resolution. Adverse reactions recorded in eDiaries beyond Day 7 should be reviewed either via phone call or at the following study visit. Participants will be given thermometers to record their body temperatures and rulers to measure any injection site reactions.

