8.6. Physical Examination and Vital Signs

A full physical examination, including height and weight, will be performed at the Screening Visit; symptom-directed physical examinations may be performed at other clinic visits. Interim

physical examinations will be performed at the discretion of the investigator. Any clinically significant finding identified by a healthcare professional during clinic visits should be reported as a MAAE ([Section 8.10.4](#)).

Vital sign measurements include the assessment of systolic and diastolic blood pressures, heart rate, respiratory rate, and body temperature. The preferred route of temperature assessment is oral. On the day of vaccination, vital signs will be collected once prior to vaccination and once 15 minutes after vaccination. Vital signs may be collected at other clinic visits in conjunction with a symptom-directed physical examination.

The information collected will be recorded in the eCRF.

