8.10.4. Medically Attended Adverse Events

A MAAE is an AE that leads to an unscheduled visit to an HCP. This would include visits to a clinic for unscheduled assessments (eg, rash assessment, abnormal laboratory follow-up,

COVID-19) and visits to HCPs external to the clinic (eg, urgent care, primary care physician). Investigators will review unsolicited AEs for the occurrence of any MAAEs. Unsolicited AEs will be captured on the AE page of the eCRF.

All PCR-confirmed COVID-19 cases will be recorded as MAAEs under the AE term of “COVID-19.” Cases of participants who test positive using an approved/authorized lateral flow/rapid antigen test and report symptoms of COVID-19 as defined by the NHS or the CDC ([Section 8.9.2](#)) but test negative by PCR or are unable to obtain PCR testing within 2 weeks of symptom onset will be recorded as an AE.

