8.10.12. Time Period and Frequency for Collecting AE and SAE Information

Medical occurrences that begin before the start of IP administration but after obtaining informed consent will be recorded in the Medical History/Current Medical Conditions section of the eCRF and not in the AE section; however, if the condition worsens at any time during the study, it will be recorded and reported as an AE.

AEs may be collected as follows:

- Observing the participant
- Receiving an unsolicited complaint from the participant
- Questioning the participant in an unbiased and nonleading manner

All SAEs will be recorded and reported to the Sponsor or designee immediately and under no circumstance should this exceed 24 hours of becoming aware of the event, as indicated in [Section 8.10.2](#). The investigator will submit any updated SAE data to the Sponsor within 24 hours of it being available.

Investigators are not obligated to actively seek AEs or SAEs after conclusion of the study participation (EoS). However, if an investigator learns of any SAE, including a death, at any time after a participant has completed or withdrawn from the study and considers the event to be reasonably related to the study IP or study participation, the investigator must promptly notify the Sponsor.

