6.3.1. Adverse Events

A treatment-emergent AE (TEAE) is defined as any event occurring during the study that was not present before exposure to study vaccine, or any event already present that worsens after exposure to study vaccine. Worsening of a pre-existing condition after vaccination will be reported as a new AE.

Adverse events will also be evaluated by the investigator for the coexistence of MAAE which is defined as an AE that leads to an unscheduled visit to a healthcare practitioner.

Refer to Protocol Appendix 3 for the definitions of AEs of special interest (AESI).

Analyses of unsolicited AEs will be summarized by stage, up to 28 days after vaccination and throughout the study and by treatment group ([Section 6.1](#)).

All summary tables (except for the overall summary of AEs) for unsolicited AEs will be presented by SOC and PT for TEAEs with counts of participants included. When summarizing the number and percentage of participants with an event, participants with multiple occurrences of the same AE or a continuing AE will be counted once. Participants will be presented according to the highest severity (the strongest causality) in the summaries by severity (of related AEs), if participants reported multiple events under the same SOC and/or PT.

Percentages will be based upon the number of participants in the Safety Set.

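### The MAAE has two incompatible rules, so findings at scheduled visits that lead to no unscheduled visit may be counted in a primary safety endpoint component, contrary to its definition

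*Protocol*

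**What the plan says.** **Definition.** Protocol 8.10.4 states: "A MAAE is an AE that leads to an unscheduled visit to an HCP". It brings in attendance at a clinic only for assessments outside the schedule: "This would include visits to a clinic for unscheduled assessments". SAP 6.3.1 uses the same definition: "defined as an AE that leads to an unscheduled visit to a healthcare practitioner".

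**Reporting instruction.** Note 3 to the protocol's schedules of events, in both parts, reads: "Any clinically significant finding identified by a healthcare professional during a study visit should be reported as a MAAE". SAP Appendix E repeats it under Tables 10 and 11. Protocol 8.6 says: "Any clinically significant finding identified by a healthcare professional during clinic visits should be reported as a MAAE". It refers the reader to 8.10.4, which contains no such rule.

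**Events designated directly.** Protocol 8.10.4 makes PCR-confirmed COVID-19 an MAAE, and 8.10.5.1 does the same for suspected anaphylaxis.

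**Use.** MAAEs from Day 1 to end of study are listed among the primary safety endpoints in protocol Section 3 and SAP 3.1.2. SAP 6.3.1.1 and 6.3.1.2 tabulate them as treatment-emergent events, overall and by system organ class and preferred term.

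**Collection window.** Under protocol 8.10.7, ordinary unsolicited AEs are collected for 28 days. MAAEs, SAEs, AESIs and AEs leading to withdrawal are collected until participation ends.

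**The concern.** The definition turns on what the event made the participant do, namely attend a practitioner outside the schedule. The instruction turns on what a professional noticed at a visit that may have been planned anyway. A finding can satisfy the second and fail the first, yet both carry the same label and feed the same table rows.

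The safety objective is descriptive, so the level and meaning of the MAAE rate are the result. If sites apply different rules, the rate mixes events that prompted medical attendance with findings from the trial's own visits, and no planned output separates them.

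**Working it through.** The documents state no figure for this point, so the check sets the passages side by side.

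**1. Where the rules can diverge.** Note 3 places symptom-directed examinations after vaccination at Days 29, 85, 179 and 359, at unscheduled visits and, in Part 2, at Day 8 where applicable. At an unscheduled visit prompted by the event, both rules give the same answer. They can diverge at the scheduled visits.

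**2. Applying each rule to simple records.**

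| Record | Protocol 8.10.4, SAP 6.3.1 | Note 3, protocol 8.6 |
|---|---|---|
| Enlarged node found at the scheduled Day 29 examination, no further visit | Not an MAAE | MAAE |
| Same node, participant then sees a GP because of it | MAAE | MAAE |
| Event that brings the participant to an unscheduled visit | MAAE | MAAE |
| Murmur found at Screening or before dosing on Day 1 | Not an MAAE | Labelled MAAE, but outside the treatment-emergent tables |

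The first row is the conflict. The last is only a conflict of recording instructions, because protocol 8.10.12 says: "Medical occurrences that begin before the start of IP administration but after obtaining informed consent will be recorded in the Medical History/Current Medical Conditions section".

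**3. Whether anything settles it.** The SAP introduction lets the SAP prevail over the protocol on methods, but the SAP carries both rules, one in 6.3.1 and one in Appendix E. Protocol 8.10.4 names the category it adds, PCR-confirmed COVID-19, and does not add findings from scheduled examinations. No table rule separates the two kinds of report.

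**4. When it matters most.** The 28-day window is the day of injection plus 27 days, so study days 1 to 28. The Day 29 visit is allowed from 29 − 3 = 26 to 29 + 7 = 36, so a finding dated at that visit can fall on either side of the limit. Days 85, 179 and 359 are all beyond it. There, a finding that is not serious, not an AESI and not a cause of withdrawal enters mainly through the MAAE label. A site following note 3 records it; a site following 8.10.4 may not. The choice of rule can then decide whether the finding is captured at all.

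**5. Size.** The inputs needed are the share of participants per scheduled visit with such a finding and no unscheduled visit, and the share of those with no other MAAE. The documents give neither, so no number of extra MAAEs can be derived.

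**6. Inference.** Protocol Table 12 plans counts and percentages for MAAEs with no confidence interval, and no hypothesis is attached to them. Alpha, power and sample size are untouched.

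**The case against.** The strongest reply is that this is a loose cross-reference with little consequence. The same instruction applies to both arms of a 1:1 randomisation, and assessments in Phase A are made by blinded staff. The post-vaccination examinations are symptom-directed, and 8.6 makes them optional, so they are not repeated full screens of every participant. SAP 6.3.1 has the investigator evaluate AEs against the narrow definition, and 8.10.4 has investigators review unsolicited AEs for MAAEs. The protocol also creates MAAEs by designation elsewhere, and note 3 could be meant as one more such extension. Finally, 8.10.10 states a general duty to report AEs seen during the study, so a late finding might be recorded anyway.

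Much of this stands, and it rules out several stronger readings that a reader might infer:

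- *Events with no medical attendance are counted.* Not supported. Note 3 requires a healthcare professional to identify the finding; what may be missing is an unscheduled visit.
- *Sites must report these findings, and they will be counted.* The text says should, and SAP 6.3.1 applies the narrow definition. The documents support only that they may be counted.
- *Findings before dosing inflate the endpoint.* They go to medical history, AEs before dosing are analysed separately under 8.10.7, and the MAAE rows are limited to treatment-emergent events.
- *The arms are biased against each other.* Nothing in the documents makes the rule depend on arm.

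The reply does not remove the conflict. If note 3 is a deliberate extension, neither 8.10.4 nor SAP 6.3.1 says so, and the general duty in 8.10.10 sits beside an explicit 28-day limit in 8.10.7.

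**Conclusion.** The conflict is real and nothing in the documents resolves it. Post-vaccination findings at scheduled visits that lead to no unscheduled visit may be reported and counted as MAAEs, contrary to the definition of this primary safety endpoint component. The count can vary with the rule each site follows. After the 28-day window, that choice can also decide whether a non-serious, non-AESI finding is collected.

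The effect is on the level and meaning of a descriptive rate. A reader might be tempted to size it by assuming a per-visit rate and compounding it over the scheduled examinations. The rate would be invented, visits would have to be independent with no dropout, and the result would be an upper limit wherever participants have another MAAE. The conclusion does not need such a figure.

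It rests on two assumptions: that some clinically significant findings at scheduled visits lead to no unscheduled visit, and that the tables use the MAAE label as reported, since no separating rule is given. The plan should be corrected, but the comparison between arms is not evidently threatened.

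**What to change.** Reconcile schedule note 3 (protocol Tables 1 and 2, SAP Tables 10 and 11), protocol 8.6, protocol 8.10.4 and SAP 6.3.1 to one definition: an AE leading to an unscheduled visit to a healthcare practitioner, plus the events the protocol explicitly designates (PCR-confirmed COVID-19 and suspected anaphylaxis). The designated events must be named. Otherwise a COVID-19 case confirmed by a swab at a scheduled visit could drop out of the MAAE rows, contrary to 8.10.4.

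Keep collecting clinically significant post-vaccination findings from scheduled visits to end of study, and state this in 8.10.7 as an explicit exception to the 28-day unsolicited AE window. A flag alone would not create a collection category, and late safety findings could be lost. Flag these records 'identified at scheduled study visit' and tabulate them on a separate line from the MAAE rows.

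For records already entered, classify by the reported reason for attendance and query unclear cases. Dates alone are not reliable: onset may precede detection, and an event reported at a scheduled visit may already have led to a GP visit.

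The cost is wording in both documents, one eCRF flag, some queries and one extra table row.
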